#### 28.2. Economic evaluation

Given that most of the economics data will be collected in disaggregated form, the statistical analyses will follow those for the cluster RCT data - taking account of the cluster design of the trial and of any further skewness in the costs. Beyond this, the approach will be to assess whether the intervention is unambiguously efficient - leading to improvements in dietary behaviour with no impact on net costs (or profits) in the different sectors concerned. If this is not the case, the trade-offs between sectors in terms of costs and outcomes will be made explicit along with an assessment of their magnitudes.

#### 28.3. Process evaluation

#### 28.3.1. Quantitative element

The EPOS data will be analysed using standard data mining measures for basket analysis – a modelling technique that identifies products commonly purchased together.(21)

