#### 8. STUDY OBJECTIVES

The primary objective is to answer the question: does the C4L c-store FFV intervention lead to a statistically significant increase in consumption of FFV over 12 months among regular users of intervention stores, compared to regular users of control stores?

Secondary objectives will be to answer the questions:

- What is the effect of the intervention at 12 months on change in other markers of dietary quality among regular users of intervention stores, compared to regular users of control stores?
- What are the resource consequences of the intervention at 12 months and how do they relate to intervention outcomes?
- What is the effect of the intervention on change in shopping habits at 12 months among regular users of intervention stores, compared to regular users of control stores?
- What is the effect of the intervention at 1 and 12 months on change in sales variety, cost and quality of FFV in intervention stores, compared to control stores?
- What variation is there in implementation of the intervention at 1 and 12 months?
- What is the feasibility, acceptability and unexpected consequences of the intervention at 8-10 months among key stakeholders including consumers, retail sector personnel (store managers and owners, instore Fresh Food Champions (see section 18.1.2), and other staff) and intervention implementation professionals (decision makers from the Department of Health, the Association of Convenience Stores and the symbol groups involved in the intervention)?

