#### 20.3.1. Stores

At the store level, the primary quantitative marker of process will be change in sales of FFV measured as total turnover from FFV per week using EPOS data provided by store managers over one week at baseline, one month and 12 month follow up. These data are collected by electronic bar-code scanners already installed in stores. Secondary markers of process measured using EPOS data will be change in range of FFV sold, change in proportion of total sales accounted for by FFV, and change in proportion of baskets that include FFV. Secondary markers of process, measured from data collected during in-store observations at baseline, one month and 12 month follow up, will be change in:

- variety of FFV available, measured as the number of different FFV lines on sale
- cost of FFV, measured as the proportion of FFV lines on sale at below the median price for that line across all stores in the study
- quality of FFV, measured as proportion of FFV lines on sale judged by appearance to be of good quality

In intervention stores we will also assess fidelity and standard of the implementation of the intervention at baseline, one month and 12 month follow up, using in-store observations and a data collection instrument covering key aspects of intervention implementation derived from the guidance and documentation provided to store managers with C4L materials. We will also take digital photographs of the inside and outside of study stores to keep a permanent visual record of the use of C4L branded materials and FFV displays.

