#### 23.3. Process evaluation

#### 23.3.1. Quantitative element

Collection of shopping habits data is detailed in sections 23.1.1 and 23.1.2. The other aspects of the quantitative process evaluation are analyses of EPOS data and in-store observations. Information on sales of FFV over one week at baseline, one month and 12 month follow up will be provided by store managers from their EPOS records.

Information on available FFV will be assessed by direct observation by researchers visiting individual stores. An in-store observation instrument will be used to collect data at baseline; one and 12 month follow up to assess variety, cost and quality of FFV and to assess how the intervention has been implemented in intervention stores at one and 12 month follow up. With store managers' permission, we will also take digital photographs of the inside and outside of study stores to keep a permanent record of use of C4L branded materials and FFV displays. Cost comparison data will be accessed via web based searches of a major high street retailer's on-line store for the costs of a comparable range of FFV to that currently available in the study c-store within eight days of each individual c-store visit.

Although researchers will make themselves known to managers on arrival for observations and seek permission to conduct observations, these visits will be unannounced.

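### The only analysis named for EPOS data in the process evaluation is basket analysis, which does not estimate the store-level primary marker (change in weekly FFV turnover) or its difference between arms

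*Protocol*

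**What the plan says.** Four parts of the protocol bear on the point.

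- **Objective (Section 8).** One secondary objective asks for the effect at 1 and 12 months "on change in sales variety, cost and quality of FFV in intervention stores, compared to control stores". A comma seems to be missing after the word sales; Section 9.1.3 lists sales as an item separate from variety, cost and quality.
- **Marker (Section 20.3.1).** At store level, "the primary quantitative marker of process will be change in sales of FFV measured as total turnover from FFV per week", taken from electronic point of sale (EPOS) records. The secondary EPOS markers are "change in range of FFV sold, change in proportion of total sales accounted for by FFV, and change in proportion of baskets that include FFV". On timing, Section 23.3.1 says: "Information on sales of FFV over one week at baseline, one month and 12 month follow up will be provided by store managers".
- **Analysis (Section 28.3.1).** The section is one sentence: "The EPOS data will be analysed using standard data mining measures for basket analysis", which it explains as "a modelling technique that identifies products commonly purchased together".
- **Integration (Section 28.4).** EPOS data are listed among the sources for examining store-level change in FFV sales and costs, within each arm and across arms. No estimator, model or adjustment is given.

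**The concern.** The protocol sets a quantity to estimate (change in weekly FFV turnover), a contrast (intervention against control stores) and two time points. It then assigns the data to a technique that, as the protocol itself describes it, answers another question: which products appear together in a basket. An analyst who followed Section 28.3.1 literally would report co-purchase patterns and no estimate of the sales effect.

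This matters for interpretation. Section 7.1 reports that earlier evaluations suggested higher FFV sales, while the effect on consumption was unknown. Whether FFV sales rose in intervention stores relative to control stores is an early link in reading the consumption result. If consumption does not change, one needs a randomised estimate of the sales effect to tell whether sales failed to rise or rose without a matching rise in intake.

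**Working it through.** The protocol states no power, sample size or precision for the EPOS markers, so there is no figure to reproduce. The check compares sections and then tests whether basket measures can stand in for turnover.

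**1. Does any other section supply the method?**
- Section 28.1.2 gives a multilevel model, but states it for individual FFV intake, the primary outcome.
- Section 28.2 carries the cluster RCT approach over to the economic data. That may reach store revenue from EPOS (Section 20.2), but not the FFV sales marker of the process evaluation.
- Section 28.4 states the intention to compare arms, without a method.
- Section 28.3.1 is therefore the only place where an analysis of EPOS data for the process evaluation is named.

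**2. Can basket measures identify turnover?** The data here are invented for illustration. Take 1,000 baskets in a week: 60 with FFV and another item M, 40 with FFV but not M, 400 with M but not FFV, and 500 with neither. FFV spend is £1.50 per FFV basket.
- Support of FFV = (60 + 40)/1,000 = 0.10
- Joint support of FFV and M = 60/1,000 = 0.06
- Confidence, M to FFV = 60/(60 + 400) = 0.130
- Lift = 0.06/(0.10 × 0.46) = 1.304
- FFV turnover = 100 × £1.50 = £150

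Now change the week in two ways.
- Double every type of basket: FFV turnover = 200 × £1.50 = £300. All four measures are unchanged, since numerators and denominators double together.
- Keep the volume and double the price: FFV turnover = 100 × £3.00 = £300. Again all four are unchanged.

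The marker in Section 20.3.1 can therefore double with no movement in the basket measures. The example is chosen to show this. If sales rose because a larger share of baskets contained FFV, support would rise too, but it still would not give the change in turnover.

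**3. Is there an arm contrast?** Support, confidence and lift describe one set of baskets. None contains a comparison with control stores, a baseline adjustment or any use of the design, in which stores are paired within strata (Section 21.1.1) and randomised within pairs (Section 22).

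**4. What can a store-level comparison deliver?** Section 14.1.1 gives 28 stores, 14 per arm. An unadjusted two-sample t-test with 14 per arm, two-sided 5% level and 80% power detects a difference of 1.10 between-store standard deviations. Such a comparison is imprecise, which favours baseline adjustment and reporting an interval. The choice between pair and strata also has a cost: with 14 pairs as fixed effects, arm and baseline, the residual degrees of freedom are 28 − (1 + 13 + 1 + 1) = 12.

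**The case against.** The strongest reply is that the arm comparison is planned: Section 20.3.1 defines the marker and its time points, Section 28.4 says sales changes will be examined across arms, and Section 28.1.2 makes all testing beyond the primary outcome informal. On that view only the model is missing, and a protocol may leave that to a statistical analysis plan. This stands in part. A reader who infers that no between-arm look at sales is intended goes too far. But Section 28.3.1 is not silent. It names an analysis, and that analysis does not fit the marker; a later plan that followed it would carry the mismatch forward. Informal interpretation still needs an estimate of the right quantity.

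Four further readings are tempting and not supported.

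- **That the whole secondary objective is left unanswered.** Variety, cost and quality of FFV on sale come from in-store observation (Sections 20.3.1 and 23.3.1). Only the sales part depends on EPOS data.
- **That basket analysis is of no use for these markers.** The proportion of baskets containing FFV is the support of FFV, a basic basket measure and one of the listed secondary markers. Its comparison between arms is what remains unspecified.
- **That a better EPOS analysis would settle displacement.** Section 7.1 raises displacement from other outlets, and wastage. A study store's own sales records cannot show purchases lost elsewhere; the shopping habits questionnaire (Section 20.3.2) and the food diaries (Section 19) bear on that.
- **That one week per time point should be lengthened.** The protocol gives no week-to-week variance and does not say that longer records are available. Baseline is immediately before implementation (Section 18.4.2), so a window spanning that point would put post-implementation weeks into the baseline of intervention stores.

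**Conclusion.** The point holds as an internal mismatch. Section 28.3.1 names a method that does not estimate the store-level primary process marker in Section 20.3.1 and does not produce the contrast asked for in Section 8, while Section 28.4 intends that contrast without saying how to obtain it. The conclusion rests on the protocol's own description of basket analysis; the invented example only illustrates it.

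The importance is moderate. It concerns the sales part of one secondary objective in a process evaluation, and neither the primary outcome nor its analysis is affected. It should be corrected before analysis, because as written the only named EPOS analysis cannot answer the sales question.

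**What to change.** Amend Section 28.3.1 to state that:

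- FFV turnover at 1 month and at 12 months, and each secondary EPOS marker, will be compared between arms at store level (28 stores, 14 per arm);
- each comparison will adjust for the store's baseline value and for either the randomised pair or the stratification variables, with the choice fixed before the data are seen;
- results will be given as an estimate with a 95% CI, on a scale that copes with skewed turnover and with any store-week of zero FFV sales (a plain logarithm does not handle zeros);
- interpretation will be informal, in line with Section 28.1.2;
- basket analysis will be kept as a descriptive supplement.

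Add a cross-reference from Section 28.4 to this paragraph, and insert the missing comma in the Section 8 objective so that sales is clearly a separate item.

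The cost is one paragraph and a few simple regressions on data already planned. No new data collection or change to the extraction weeks is needed.

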#### 28.3.2. Qualitative element

Focus group and interview transcripts will be electronically organised according to themes specified in the topic guides and emergent from the data. Transcript tables will then be examined in-depth to identify key patterns of, and divergent, responses. At least two researchers will be involved in the analysis, and any differences of interpretation will be resolved through discussion or involvement of other members of the research team. Verbatim anonymous quotes will be used to illustrate findings.

# 28.4. Integration of results and final interpretation

Results from the cluster RCT, the economic evaluation and the process evaluation will be considered together in order to judge the impact of the intervention on c-stores and their users. Three sources of quantitative data will be used to explore changes at store level between and within study arms: EPOS data, showing changes in FFV sales and FFV costs; difference in intervention implementation using in-store observations; and retail mapping using Institute of Grocery Distribution data (to demonstrate any major changes in local retail landscape). Data from a number of sources will contribute to the economic evaluation. In particular, data will be integrated from food diaries, the food shopping questionnaire and EPOS data on food cost. The qualitative data will be used to explore our findings from the quantitative and economic analyses, including any differences in effects between stores and areas.

#### 29. ETHICS APPROVAL

Ethics approval will be sought from Newcastle University Faculty of Medicine Ethics Committee for all components except the qualitative process evaluation. Ethics approval for the qualitative process evaluation will be sought from Stirling University.

#### **30. RESEARCH GOVERNANCE**

Newcastle University will act as the sponsor for this research. The research will be overseen by a Independent Trial Steering Committee (ITSC) in line with the MRC Guidelines for Good Clinical Practice in Clinical Trials.(22) The composition of the ITSC will be:

- [name] (independent expert chair)
- [name] (independent member)
- One further member, to be confirmed (independent member)
- [name], Newcastle University (co-applicant, research manager)
- [name], Newcastle University (co-applicant, lead for analysis of nutritional data)
- [name], Stirling University (co-applicant, lead for qualitative aspects of the process evaluation)
- [name], National Centre for Social Research (co-applicant, NatCen liaison and lead for cluster RCT participant recruitment and assessment)
- [name], Glasgow Caledonian University (co-applicant, lead for economic evaluation)
- [name], Stirling University (co-applicant, lead for quantitative aspects of the process evaluation)
- [name], Cambridge University (co-applicant, HNR Cambridge liaison and lead for input of nutritional data)
- [name], Association of Convenience Stores (implementation manager of the c-store C4L FFV intervention programme for DH and ACS)
- [name], Department of Health (budget holder for the c-store C4L FFV intervention programme within DH)
- [name], Newcastle University (co-applicant, trial statistician and representative of Newcastle Trials Unit)
- [name], Newcastle University (principal applicant, chief investigator)
- Representative of the public recruited through INVOLVE

Observers from the funders will be invited to all ITSC meetings and all ITSC papers and reports will be copied to them.

Management of the study will be overseen by a study management committee, including all investigators and representatives of the intervention team.

Both the ITSC and study management committee will meet on four occasions during the course of the study.

Day-to-day management of the study will be guided from the team based at Newcastle University meeting at least monthly.

# 31. TRIAL WEBSITE

None. As we do not want to alert individual cluster RCT participants to the intervention being evaluated, we will not develop a trial website aimed at participants.

# 32. PUBLICATIONS

None as yet.

#### 33. PUBLICATION POLICY

All applicants, and study researchers, will be eligible for authorship of all papers but final authorship will be determined using the Vancouver criteria. In addition to a final report to the funders, we envisage the

following publications in peer-reviewed journals (with responsibility for leading, or identifying a lead, as indicated):

- 1. A protocol paper ([name], co-applicant and project manager).
- 2. A results paper describing the effect of the intervention on the primary and secondary dietary outcomes ([name], principal applicant).
- 3. A results paper describing the quantitative process evaluation ([name], co-applicant and lead for quantitative process evaluation).
- 4. A results paper describing the qualitative process evaluation ([name], co-applicant and lead for qualitative process evaluation).
- 5. A results paper describing the economic evaluation ([name], co-applicant and lead for economic evaluation).

# 36. CONSORT FLOW DIAGRAM, CLUSTER RCT

*Note.* All numbers shown here are estimates. Where numbers are represented by x or y, reasonable estimates cannot be made at this stage.

#### 37. FLOW DIAGRAM SHOWING ALL STUDY COMPONENTS

# 38. TIMELINE

Activity 1	re	Staff cruitme	ent		nics roval			indivi	ect & re iduals, ntrol ste	3 inter	ventio	n & 3	ch	seline o ecking ning, cl RCT	&					coll indiv	ection iduals,	n follov from cl 3 inter ores p	uster F ventio	RCT n & 3	ch	onth for up data ecking ning, cl RCT	a   &		a analy			Data pretation portin	
Activity 2	(	Externa contrac nalisati	t			Sel- reco rando sto	ruit, omise	Baseline data collection from cluster RCT individuals, 3 intervention & 3 control stores per month*			Pilot focus groups and individual in- depth interviews				Select & recruit qualitative process evaluation participants, 1 intervention & 1 control store per month						Transcription & analysis of focus group and individuals interview data					Data analysis , quantitative process evaluation							
Activity 3				confi m	rm acc ethods	roups feeptabiles; finalisment to	ity of se	In-store baseline data collection, 3 intervention & 3 control stores per month*							Focus group and individuals in- depth interviews, 1 intervention & 1 control store per month				Implement intervention, control stores, 3 stores per month*						Data analysis, economic evaluation								
Activity 4						amplin strateg	_	Implement intervention intervention stores, 3 sto per month*						data colle			collect	2 month follow up ction, 3 intervention I stores per month*															
Activity 5									In-store 1 month data collection, 2 ir & 2 control stores p		! intervention																						
Milestone			1		2		3, 4					5, 6	7	8								9		10		11				12			13
Month	-3	-2	-1	1	2	3	4	5	6	7	8	9	10	11	12	13	14	15	16	17	18	19	20	21	22	23	24	25	26	27	28	29	30
	May 10	June 10	July 10	August 10	September 10	October 10	November 10	December 10	January 11	February 11	March 11	April 11	May 11	June 11	11 yluC	August 11	September 11	October 11	November 11	December 11	January 12	February 12	March 12	April 12	May 12	June 12	July 12	August 12	September 12	October 12	November 12	December 12	January 13

\*3 stores per month for first four months and 2 stores in the final month

All elements Cluster RCT Process evaluation Economic evaluation Intervention implementation Milestones
--

# **39. MILESTONES**

Milestone	Description	Completion date	Milestone	Description	Completion date
1	All staff & contracts in place	End July 10	8	One month follow up data collection from all stores (quantitative process evaluation) complete	End June 11
2	All approvals in place	End September 10	9	All focus groups and individual interviews complete	End January 12
3	Consent from all study stores obtained	End November 10	10	12 month follow up data collection for all individuals & stores (cluster RCT & quantitative process evaluation) complete	End April 12
4	All methods finalised	End November 10	11	Intervention implemented in all control stores	End June 12
5	Consent from all individuals (cluster RCT) obtained	End April 11	12	All analyses complete	End October 12
6	Baseline data collection from all individuals & stores (cluster RCT & quantitative process evaluation) complete	End April 11	13	Reporting complete	End January 13
7	Intervention implemented in all intervention stores	End May 11			

#### **40. STUDY DOCUMENTATION APPENDICES**

A number of documents are provided as appendices. These are grouped under the headings of the components of the study they relate to.

#### 40.1. Cluster RCT & quantitative process evaluation documents (all provided at this stage)

- A1 Letter to ACS regional managers about the study
- A2 Consent form for regional managers to take part
- A3 Letter to stores about the study
- A4 Information sheet for stores describing the research process
- A5 Consent form for store managers to take part
- A6 a Letter to stores concerning allocation to intervention (now) group b Letter to stores concerning allocation to control (later) group
- A7 Information sheet for customers
- A8 Consent form for customers
- A9 Letter (6 months) to customers concerning retention
- A10 Change of address and circumstances form for customers (base and six months)
- A11 Letter to customers at 12 months concerning arrangements for follow up data collection
- A12 Change of address form for customers at 12 months
- A13 DRAFT feedback to participants
- A14 Socio-demographic questions (for computer based questionnaire)
- A15 Shopping habits questions (for computer based questionnaire)
- A16 Shopping habits reminder card
- A17 Food and drink diary instructions
- A18 Food and drink diary
- A19 Diary interviewer assessment schedule
- A20 Diary Evaluation
- A21 Diary reminder card
- A22 Diary packaging card
- A23 In-store implementation observation check list
- A24 IHS Interviewer safety
- A25 IHS Interviewer Safety Chart
- A26 IHS Interviewer safety record sheet
- A27 NatCen III Working safely Oct 2008
- A28 NatCen V risk assessment Oct 2008
- A29 NatCen Unsafe Areas Oct 2008
- A30 IHS Code of confidentiality

Version 1 Page 24 of 25

